6.1.4.8 Management of hepatitis reactivation

6.1.4.8.1 Monitoring for hepatitis B reactivation

Hepatitis B reactivation has been observed in patients receiving everolimus treatment.

Table 6-3 provides details of monitoring according to screening/baseline results of viral load and serologic markers testing.

Table 6-3 Monitoring for positive baseline hepatitis B results

Test	Result	Result	Result	Result	Result
HBV-DNA	Positive	Positive or negative	Negative	Negative	Negative
HBsAg	Positive or negative	Positive	Negative	Negative	Negative
HBsAb	Positive or negative	Positive or negative	Positive and no prior HBV vaccination	Positive or negative	Negative or positive with prior HBV vaccination
HBeAb	Positive or negative	Positive or negative	Positive or negative	Positive	Negative
Recommendation	Patient does not qualify for the study.		No prophylaxis. Monitor HBV-DNA every 4 weeks (\pm 1 week)*		No specific action

* The monitoring for hepatitis B reactivation has to be performed in all patients, irrespective of the treatment arm they have been assigned to (thus, not only in patients taking everolimus alone or in combination, but also in patients on pasireotide alone), taking into account the results arising from the four hepatitis B tests. However, in light of evidence that the risk for hepatitis B reactivation is related to everolimus, the drug interruption/discontinuation strategy (see Table 6-4) will apply to everolimus only.

For hepatitis B reactivation, definition and management guidelines see Table 6-4.

Table 6-4 Guidelines for management of hepatitis B

HBV reactivation (with or without clinical signs and symptoms)*	Actions
For patients with baseline results: Negative HBV-DNA and HBs-Ag AND Positive HBs-Ab (with no prior history of vaccination against HBV), OR positive HBe-Ab ----- Reactivation is defined as:	Treat: Start first antiviral medication AND Interrupt everolimus administration until resolution: \leq baseline HBV-DNA levels If resolution occurs within <28 days , the study drug should be re-started at one dose lower, if available. If the patient is already receiving the lowest dose of study drug according to the protocol, the patient should restart at the same dose after resolution. Antiviral therapy should

HBV reactivation (with or without clinical signs and symptoms)*	Actions
New appearance of measurable HBV-DNA	continue at least 4 weeks after last dose of study drug. If resolution occurs after ≥28 days , patients should discontinue study treatment but continue antiviral therapy for at least 4 weeks after last dose of study drug.
*All reactivations of hepatitis B are to be recorded as grade 3 (CTCAE v 4.0 Metabolic Laboratory/Other: Viral Re-activation), unless considered life threatening by the investigator; in this case, they should be recorded as grade 4 (CTCAE v 4.0 Metabolic Laboratory/Other: Viral Re-activation). Date of viral reactivation is the date on which both DNA and ALT criteria were met (e.g. for a patient who was HBV-DNA positive on 01-JAN-10 and whose ALT reached ≥ 5 × ULN on 01-APR-10, the date of viral reactivation is 01-APR-10).	

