6.1.1.1 Pasireotide LAR administration

Pasireotide LAR 60 mg will be administered as an i.m. depot injection once every 28 days (+/- 3 days) starting at Day 1 (visit 2).

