If such withdrawal occurs, or if the patient fails to return for visits, the investigator must determine the primary reason for a patient's premature withdrawal from the study and record this information on the CRF.

All patients who discontinue study treatment must have safety evaluations 56 days after the last dose of pasireotide LAR or everolimus, whichever comes last.

All cancer medications/therapies given to a patient up to 56 days after the last dose of study treatment must be recorded in the CRF.

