8.1 Adverse events

8.1.1 Definitions and reporting

An adverse event is defined as the appearance of (or worsening of any pre-existing) undesirable sign(s), symptom(s), or medical condition(s) that occur after patient's signed informed consent has been obtained. Abnormal laboratory values or test results occurring after informed consent constitute adverse events only if they induce clinical signs or symptoms, are considered clinically significant, require therapy (e.g., hematologic abnormality that requires transfusion or hematological stem cell support), or require changes in study medication(s).

Adverse events that begin or worsen after informed consent should be recorded in the Adverse Events CRF. Conditions that were already present at the time of informed consent should be recorded in the Medical History page of the CRF. Adverse event monitoring should be continued for at least 56 days following the last dose of study treatment. Adverse events (including lab abnormalities that constitute AEs) should be described using a diagnosis whenever possible, rather than individual underlying signs and symptoms. When a clear diagnosis cannot be identified, each sign or symptom should be reported as a separate Adverse Event.

Adverse events will be assessed according to the Common Terminology Criteria for Adverse Events (CTCAE) version 4.0. If CTCAE grading does not exist for an adverse event, the severity of mild, moderate, severe, and life-threatening, corresponding to Grades 1-4, will be used. CTCAE Grade 5 (death) will not be used in this study; rather, information about deaths will be collected through the "Study evaluation completion – Core" form.

The occurrence of adverse events should be sought by non-directive questioning of the patient (subject) during the screening process after signing informed consent and at each visit during the study. Adverse events also may be detected when they are volunteered by the patient (subject) during the screening process or between visits, or through physical examination, laboratory test, or other assessments. As far as possible, each adverse event should be evaluated to determine:

1. The severity grade (CTCAE grade 1-4);
2. Its duration (Start and end dates);
3. Its relationship to pasireotide LAR or everolimus or combination pasireotide LAR and everolimus (Reasonable possibility that AE is related: No, Yes);

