8.1.2 Laboratory test abnormalities

8.1.2.1 Definitions and reporting

Laboratory abnormalities that constitute an Adverse event in their own right (are considered clinically significant, induce clinical signs or symptoms, require concomitant therapy or require changes in study treatment), should be recorded on the Adverse Events CRF. Whenever possible, a diagnosis, rather than a symptom should be provided (e.g. anemia instead of low hemoglobin). Laboratory abnormalities that meet the criteria for Adverse Events should be followed until they have returned to normal or an adequate explanation of the abnormality is found. When an abnormal laboratory or test result corresponds to a sign/symptom of an already reported adverse event, it is not necessary to separately record the lab/test result as an additional event.

Laboratory abnormalities, that do not meet the definition of an adverse event, should not be reported as adverse events. A Grade 3 or 4 event (severe) as per CTCAE does not automatically indicate a SAE unless it meets the definition of serious as defined below and/or as per investigator's discretion. A dose hold or medication for the lab abnormality may be required by the protocol and is still, by definition, an adverse event.

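### Protocol Table 6-4 defines hepatitis B reactivation by new HBV-DNA alone, but its footnote dates the event only once ALT is also raised: a DNA-only reactivation gets no footnote date, and one with a later ALT rise is dated late

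*Protocol*

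**What the plan says.** Everything at issue is in the current text of Protocol Section 6.1.4.8.1, Table 6-4.

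- **Definition.** Reactivation is "New appearance of measurable HBV-DNA". The column heading counts events whether or not they are symptomatic: "HBV reactivation (with or without clinical signs and symptoms".
- **Actions.** Start an antiviral and interrupt everolimus until HBV-DNA is back to its baseline level or lower. Both the trigger and the resolution rule use DNA only. The footnote to Table 6-3 says that the interruption and discontinuation strategy "will apply to everolimus only".
- **Recording.** The Table 6-4 footnote has every reactivation recorded as grade 3, or grade 4 if life-threatening.
- **Dating.** The same footnote says: "Date of viral reactivation is the date on which both DNA and ALT criteria were met". In its example, HBV-DNA is positive on 1 January 2010, ALT reaches 5 times the upper limit of normal on 1 April 2010, and the event is dated 1 April 2010.

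For tabulation, Protocol Sections 10.5.3.1.1 and 10.5.3.1.2 and SAP Sections 10 and 10.1 restrict the adverse event tables to events that start or worsen between the first dose and 56 days after the last dose. Later events are listed only. SAP Section 10.3 tabulates HBV-DNA results by visit and lists them with sample dates. It contains no dating rule for reactivation.

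**The concern.** The definition and the dating rule in one table use different criteria. The definition needs DNA; the date needs DNA and ALT. A patient can therefore meet the definition, be treated for it and be recorded at grade 3 while the footnote supplies no date. Where ALT rises only later, the footnote date follows the qualifying event.

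What is at stake is where the event appears in the safety report. Everolimus is the drug to which the protocol attributes this risk, and Protocol Section 1.2.2.3 mentions reactivation with fatal outcome. A start date pushed past the 56-day window would take the event out of the treatment-emergent tables and leave it in listings.

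**Working it through.** **1. The two rules side by side**

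| Element of Table 6-4 | HBV-DNA needed | ALT needed |
|---|---|---|
| Definition | yes | no |
| Start of antiviral and everolimus interruption | yes | no |
| Resolution | yes (at or below baseline) | no |
| Footnote date | yes | yes, threshold shown only in the example |

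The hepatitis C table (Table 6-5) has the same layout and the same grading footnote, with a definition based on RNA alone and no ALT dating clause. The hepatitis B dating sentence is the only element out of line.

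**2. The protocol's example**

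Footnote rule: later of the DNA date and the ALT date = later of 1 January 2010 and 1 April 2010 = 1 April 2010. This reproduces the stated date.

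Definition rule: date of first measurable HBV-DNA = 1 January 2010.

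Lag = 31 + 28 + 31 = 90 days.

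**3. The three possible cases**

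- ALT never meets the criterion: the definition gives a date; the footnote gives none.
- ALT meets it after DNA appears: the footnote date is late by the DNA-to-ALT lag.
- ALT meets it on or before the DNA date: the two rules give the same date.

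**4. Effect on the treatment-emergent tables**

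This step assumes that the site enters the footnote date as the adverse event start date. Count days from the DNA-positive sample (day 0). Then

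days past the window = lag − (day of last dose + 56).

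With the example's 90-day lag, everolimus monotherapy and no restart:

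- last dose day 0: 90 − 56 = 34 days past (the window ends 26 February 2010);
- last dose day 7: 90 − 63 = 27 days past;
- last dose day 14: 90 − 70 = 20 days past;
- last dose day 34 or later: 90 − 90 = 0 or less, so inside.

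A lag of 56 days or less cannot take the event outside if the last dose is on or after day 0.

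The no-restart condition is a path the protocol itself provides. Table 6-4 requires discontinuation if DNA resolves only after 28 days or more, and Section 6.3.1.2 requires it for any everolimus delay of 28 days or more. In that case the last everolimus dose is the one before the interruption.

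**The case against.** The strongest reply is that the adverse event rules already fix onset. Under Protocol Sections 8.1.1 and 8.1.2.1, a laboratory abnormality is an adverse event when it needs therapy or a change in study medication. New HBV-DNA triggers an antiviral and, where everolimus is given, an interruption, so the DNA result can be the onset in its own right. Nothing in the visible plan uses the footnote date: there is no time-to-reactivation analysis, and no text equates that date with the CRF start date. Much of this stands. It means that a DNA-only event lacks a footnote date, not necessarily an adverse event start date. It does not remove the problem. Section 8.1.1 asks for events to be described "using a diagnosis whenever possible, rather than individual underlying signs and symptoms", so a site would naturally record the diagnosis of reactivation, and the only text that dates that diagnosis is the footnote.

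Three stronger readings are tempting and are not supported.

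- A reader might infer that every reactivation is dated late. That holds only when ALT rises after DNA.
- A reader might infer that reactivations are in fact missing from the tables. The documents report no such event, and the 90-day lag is an illustration, not an expected delay.
- A reader might work out a margin for the combination arm from continued pasireotide injections, since post-treatment safety follow-up runs from the last "dose of pasireotide LAR or everolimus, whichever comes last". But an everolimus interruption of 28 days or more requires discontinuation, and Section 6.3.2 stops the combination when one drug is discontinued. Long continued injections without everolimus are therefore not a protocol-compliant case, and no range is given here.

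In the pasireotide monotherapy arm the interruption rule does not apply, so dosing normally continues and the event would normally be inside the window.

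It is also fair to say that the prospective value is small: the Amendment 5 rationale reports the primary analysis as done and 11 patients still in the extension phase.

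**Conclusion.** The dating sentence is wrong as written. It conflicts with the definition in its own table, depends on an ALT criterion that is never defined, gives no date to a DNA-only reactivation, and gives a date 90 days after the definition is met in the protocol's own example.

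The practical effect is minor and conditional. Loss from the treatment-emergent tables needs all of the following: a reactivation, a DNA-to-ALT lag of more than 56 days, everolimus stopped around DNA positivity and not restarted, and a site that uses the footnote date as the start date. The last of these is an inference. Under those conditions, with the example's lag and the last dose on the DNA-positive day, the event is 34 days past the window.

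Reactivations should be rare, because exclusion criterion 16 removes patients positive for HBsAg or HBV-DNA. Patient management follows the DNA definition, the primary endpoint is untouched, and the DNA date can be recovered from the SAP Section 10.3 listing.

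**What to change.** Replace the footnote's dating sentence and its example with: *the date of viral reactivation is the sample date of the first measurable HBV-DNA*. This matches the table's definition and actions and gives every reactivation a date.

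Before the extension-phase safety rerun (SAP Sections 3.4.2 and 10), compare the start date of any recorded reactivation adverse event with the HBV-DNA sample dates listed under SAP Section 10.3, and query any that differ. Because that rerun is cumulative, the check covers the core phase as well.

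No separate ALT event is needed. Where an abnormal result belongs to an event already reported, Section 8.1.2.1 says that "it is not necessary to separately record the lab/test result as an additional event".

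The cost is one footnote sentence with its example and a short check on data already held. No new data are collected.

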6.1.4.8.2 Monitoring for hepatitis C

At screening, all patients will be tested for the presence of HCV Ribonucleic acid-Polimerase Chain Reaction (HCV-RNA-PCR). If a patient tests positive for the presence of HCV-RNA-PCR, he/she will be considered ineligible for the study according to Exclusion Criterion #16.

Patients known to have a history of HCV infection, despite a negative viral load test at baseline (including those that were treated and are considered “cured”) should be monitored every 4 weeks (± 1 week) for the risk of hepatitis C reactivation.

The monitoring for hepatitis C reactivation has to be performed in all patients with a known history of HCV infection, irrespective of the treatment arm they have been assigned to (thus, not only in patients taking everolimus alone or in combination, but also in patients on pasireotide alone). However, in light of evidence that the risk for hepatitis C reactivation is related to everolimus, the drug interruption/discontinuation strategy (see [Table 6-5](#)) will apply to everolimus only.

For definition of hepatitis C reactivation and the management guidelines, see [Table 6-5](#).

[figure not shown]
Table 6-5 Guidelines for management of hepatitis C

HCV reactivation*	Actions
For patients with baseline results: Knowledge of past hepatitis C infection with no detectable HCV-RNA at screening. Reactivation is defined as: New appearance of detectable HCV-RNA.	Discontinue study treatment.
*All reactivations of hepatitis C are to be recorded as grade 3 (CTCAE v 4.0 Metabolic Laboratory/Other: Viral Re-activation), unless considered life threatening by the investigator; in this case, they should be recorded as grade 4 (CTCAE v 4.0 Metabolic Laboratory/Other: Viral Re-activation).	

6.1.4.9 Management of ECG changes

SSAs have shown an influence on cardiac signal transduction.

Pasireotide administered subcutaneously has been shown to prolong the QT interval in healthy subjects based on two Phase I studies [[CSOM230B2113](#)] and [[CSOM230B2125](#)]. Additional analysis of thorough QT study data [[CSOM230B2125](#)], including quantitative ECG beat to beat restitution analysis, showed that pasireotide does not alter cardiac repolarization in the same manner as drugs known to prolong QT that are associated with pro-arrhythmia.

In clinical studies in Cushing's disease patients, QTcF of >500 msec was observed in two out of 201 patients. These episodes were sporadic and of single occurrence with no clinical consequence observed.

Episodes of torsade de pointes were not observed in any clinical study with pasireotide.

If at any visit a QTcF > 500 msec is observed, triplicate ECGs, each 2-3 minutes apart, need to be taken approximately 1 hour after the initial ECG. The mean QTcF from the triplicate ECGs will be determined. If the mean QTcF is > 500msec, the patient will need to be closely monitored at the hospital and will have to postpone pasireotide LAR treatment until a cardiologist has re-evaluated the ECG (this can be done by the central cardiologist if the trial has one). If the cardiologist confirms a mean QTcF >500 msec, the patient has to discontinue. Otherwise and if the cardiologist confirms that at least one ECG shows a QTcF > 470msec, the cardiac assessments described for a confirmed QTcF > 470msec need to be followed (see [Figure 6-1](#)).

If at any visit a $470 \text{ msec} < \text{QTcF/mean QTcF} \leq 500\text{msec}$ is observed, the following steps need to be taken (refer to [Figure 6-1](#)):

[figure not shown]
- postpone pasireotide LAR administration;
- a cardiology consultation must be sought as soon as practical but within 7 days of the initial abnormal ECG and the cardiologist must re-evaluate the ECG (this can be done by the central cardiologist if the trial has one).
 - If a QTcF > 470msec is NOT confirmed, no further action needs to be taken, and pasireotide LAR can be restarted.
 - If a QTcF > 470msec is confirmed, a cardiologist must perform a thorough examination (such as reviewing baseline ECG, concurrent medications and performing a cardiovascular examination, including at least a cardiac auscultation) to assess the patient for cardiovascular risk factors.
 - If based upon the assessment by the cardiologist, the investigator considers that there is an acute cardiovascular safety risk and that the patient should not continue with study medication, the patient needs to be discontinued immediately (discontinuation criteria to be followed).
 - If following the examination by the cardiologist, the investigator considers that there is not an acute cardiovascular safety risk and that the patient could restart to receive study medication, a Holter ECG (24hr or 48hr depending on the study) must be recorded soon as practical but within 7 days after the initial abnormal ECG / at the next pasireotide LAR injection. The Holter-ECG must be started 30min prior to an injection of study medication.

The results of the ECGs, cardiac examination, Holter-ECGs and the recommendation by the cardiologist must be evaluated by the investigator to determine whether the patient should continue the trial or not (discontinuation criteria to be followed).

Overall, the monitoring of ECG changes has to be performed in all patients, irrespective of the treatment arm they have been assigned to (thus, not only in patients taking everolimus alone or in combination, but also in patients on pasireotide alone), taking into account the observed QTcF value. However, in light of evidence that the risk for ECG changes is related to SSA

treatment, the drug interruption/discontinuation strategy (see Figure 6-1) will apply to pasireotide LAR only.

Figure 6-1 Procedure for QTcF prolongations

6.1.4.10 Hepatic Safety Management

If any of the criteria below are observed at any scheduled or unscheduled visit the sponsor should be notified immediately upon awareness.

- ALT or AST > 3 x ULN and Total Bilirubin \geq 2 x ULN;
- ALT or AST > 5 x ULN and \leq 8 x ULN;
- ALT or AST > 8 x ULN.

ALT or AST > 3 x ULN and Total Bilirubin \geq 2 x ULN

If this criterion is met with the presence of alkaline phosphatase < 2 X ULN, the patient has to discontinue the study and continue the safety evaluations.

If this criterion is met without the presence of alkaline phosphatase < 2 X ULN, the patient has to perform a **safety follow-up procedure within 72 hours** of awareness of the abnormality (see [Figure 6-2](#)). According to the safety follow-up procedure, the investigator has to perform:

- liver-directed medical history and physical examination (i.e. assess occupational hazards, concomitant medications including OTC medications, inter-current illness, etc);
- liver function tests (LFT): ALT, AST, total bilirubin, (fractionate to direct/indirect bilirubin if total bilirubin is > 2.0 x ULN), Alb, PT (INR), ALP, and GGT;
- hepatitis screening: anti-HAV, IgM (to confirm acute Hepatitis A), HbsAg, anti-HBc, anti-HCV (if positive, PCR viral load should be assessed), anti-HEV, ANA antibodies, anti-smooth muscle anti-bodies, CMV and EBV;
- abdominal ultrasound (liver and biliary tree).

In addition, liver function tests have to be monitored **every 3-4 days** until resolution or return to baseline values.

- If ALT or AST return to less than 5 x ULN study drug can be resumed at the original dose level and the patient can continue the study.
- If ALT or AST rises above 5 x ULN at any time after study drug is resumed, then, the study drug should be discontinued immediately.
- If resolution or return to baseline does not occur after 2 weeks, the patient should be discontinued.

Overall, patients may need to be discontinued if the abnormal liver function criteria are met upon LFT retesting (See [Section 6.3.2.1](#)). Progress reports of the event should be maintained until resolution or stabilization (i.e. no further elevation after 2 consecutive assessments).

If any of these criteria are met and deemed an AE by the investigator, the event must be recorded on the AE CRF page; if the event is deemed serious by the investigator, then proceed with completing the SAE form. In addition, any significant findings from the physical examination should be recorded on the AE CRF page.

[figure not shown]
ALT or AST > 5 x ULN and < 8 x ULN

If this criterion is met, the study treatment has to be temporarily interrupted, and the patient has to perform a **safety follow-up procedure withing 72 hours** of awareness of the abnormality, as above reported (see [Figure 6-2](#)).

ALT or AST > 8 x ULN

If this criterion is met, the study treatment has to be discontinued (see [Figure 6-2](#)).

Figure 6-2 LFT Management Algorithm

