6.3.1.2 Dose modifications for everolimus

Dose adjustments are permitted for any adverse event suspected to be related to everolimus in those patients unable to tolerate the once-daily oral dose of 10 mg. If the administration of everolimus must be interrupted because of unacceptable toxicity, study drug dosing will be interrupted or modified according to the guidelines in [Table 6-7](#). If the toxicity is intolerable to the patient at the original 10 mg daily dose, interrupt everolimus until recovery to grade ≤ 1 ; then, reintroduce everolimus at the initial dose or lower dose level depending on toxicity type and grade ([Table 6-8](#)).

If a patient has already decreased 2 dose level (i.e., to 5 mg every other day), no further dose reduction is permitted. Patients who need an additional dose reduction will be required to discontinue the study drug.

The lower dose level introduced after tolerability issues will be maintained throughout the study.

The initial once-daily oral dose of everolimus (10 mg) can be administered at two different strengths: either as two 5 mg tablets, taken together QD, or as a single 10 mg tablet. In case a dose reduction is required due to toxicity, patients initially receiving the 10 mg strength will be provided with the 5 mg strength. Thus, they will be able to take the reduced 5 mg dose as a single 5-mg tablet.

Table 6-7 Everolimus dose level modification guidelines

Dose level	Dose and schedule
0 (starting dose)	10 mg daily
Decrease 1 dose level	5 mg daily
Decrease 2 dose levels	5 mg every other day

Table 6-8 Dosing modification criteria for suspected everolimus-related toxicity

Toxicity	Action
Non-hematological toxicity	
Grade 2 (except pneumonitis – refer to Table 6-2) (except blood glucose changes – refer to Table 6-1) (except Hepatitis B and C management – refer to Table 6-4 and Table 6-5) (except hepatic toxicity – refer to Figure 6-2)	If the toxicity is tolerable to the patient, maintain the same dose. Initiate appropriate medical therapy and monitor. If the toxicity becomes intolerable to patient, interrupt everolimus until recovery to grade ≤ 1 . Then, reintroduce everolimus at the initial dose. If the toxicity recurs at grade 2, interrupt everolimus until recovery to grade ≤ 1 . Then, reintroduce everolimus at the lower dose level.

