Any hematological or non-hematological toxicity requiring interruption for ≥ 4 weeks (28 days)	Discontinue everolimus.
*Grade 3 hyperlipidemia (hypercholesterolemia and/or hypertriglyceridemia) should be managed using medical therapies	

Investigator should manage anemia as medically indicated per local standards.

Patients whose treatment is interrupted or permanently discontinued due to an adverse event or abnormal laboratory value must be followed at least weekly until resolution or stabilization of the event, whichever comes first. The patients must be discontinued from the study if they require a dose delay of ≥ 28 days. All patients will be followed for adverse events and serious adverse events for 56 days following the last dose of everolimus. All interruptions or dose modifications must be recorded on the relevant section of the CRF.

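### Protocol 6.1.4.10: as printed, the restart rule in the raised-bilirubin branch with ALP at or above 2 x ULN depends on ALT/AST alone and has no bilirubin condition

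*Protocol*

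**What the plan says.** Section 6.1.4.10 lists three liver-test criteria, and for each of them "the sponsor should be notified immediately upon awareness". Under the first (ALT or AST above 3 x ULN with total bilirubin at or above 2 x ULN), ALP decides the path:

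- With ALP below 2 x ULN the patient leaves the study.
- "If this criterion is met without the presence of alkaline phosphatase < 2 X ULN", the patient has a safety work-up within 72 hours, and liver tests are then repeated every 3-4 days. Total bilirubin is in that panel.

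Three bullets follow. The restart bullet reads "If ALT or AST return to less than 5 x ULN study drug can be resumed at the original dose level". The next stops drug if ALT or AST rises above 5 x ULN after restart. The third is a time limit: "If resolution or return to baseline does not occur after 2 weeks, the patient should be discontinued". A closing sentence adds that "patients may need to be discontinued if the abnormal liver function criteria are met upon LFT retesting" and refers to Section 6.3.2.1.

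Under the second criterion (ALT or AST 5-8 x ULN), "the study treatment has to be temporarily interrupted" and the same work-up applies. Above 8 x ULN treatment is discontinued.

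**The concern.** A patient enters this branch on two abnormalities, transaminases and bilirubin. The condition for restarting looks at only one of them, and so does the stop rule after restart. A patient whose transaminases improve while bilirubin does not may be put back on the original dose with the combined signal still present.

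The general toxicity rules do not fill the gap. The grade 2 and grade 3 non-hematological rows of Table 6-8 apply "except hepatic toxicity", for which they point to Figure 6-2. Table 6-6 likewise sends liver-test changes elsewhere. Section 6.1.4.10 is therefore where an investigator would look for the answer.

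What is at stake is patient safety during a short window. Sample size, error rates and planned analyses are not affected.

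**Working it through.** The plan states no figure on this point, so the check compares rules.

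**Step 1. Which rule applies when bilirubin is at or above 2 x ULN (printed text only).**

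| ALT/AST (x ULN) | ALP < 2 x ULN | ALP >= 2 x ULN |
|---|---|---|
| 3-5 | discontinue | work-up; no interruption printed |
| 5-8 | discontinue | interrupt, then restart bullet |
| > 8 | discontinue | discontinue |

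Four cells discontinue, one has work-up only, and one leads to the restart bullet: 4 + 1 + 1 = 6. The words about returning and resuming imply an earlier interruption, so the bullet governs 1 cell of 6. Taken literally it would also cover the 3-5 cell (2 of 6), because those patients are already below 5 x ULN on entry. These are rule combinations, not patients.

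**Step 2. An illustrative patient (assumed values).** ALT 6, bilirubin 3 and ALP 2.5 x ULN: drug is interrupted under the 5-8 criterion. At a retest ALT is 4 and bilirubin is still 3. The restart condition is met (4 < 5). The combined criterion is also still met (4 > 3 and 3 >= 2).

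**Step 3. Do the discontinuation criteria catch this patient?** Sections 6.3.2.1 and 7.1.4.1 give the same three liver criteria:

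- Combined ALT/AST and bilirubin with ALP below 2 x ULN: not met, ALP is 2.5.
- ALT/AST 5-8 x ULN for more than two weeks: not met, ALT is 4.
- ALT/AST above 8 x ULN: not met.

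**Step 4. How long could re-exposure last?** Inputs: retests every 3-4 days and the two-week rule (6.1.4.10); everolimus 10 mg daily and pasireotide every 28 days (6.1.1). Assume restart on the day of the first retest and no discretionary stop. Assume also that the two weeks run from onset, and that the two-week rule counts bilirubin.

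- Retest on day 3: 14 - 3 = 11 days, or 11 x 10 = 110 mg everolimus.
- Retest on day 4: 14 - 4 = 10 days, or 10 x 10 = 100 mg everolimus.
- Pasireotide: at most one injection, if one falls due in those 14 days. With onset spread evenly over the cycle (an assumption), 14/28 = 50%.

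**Step 5. Would a longer hold breach the delay limits?** Section 6.3.1.2 removes patients who "require a dose delay of" 28 days or more; for pasireotide, 6.3.1.1 sets 56 days.

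- Everolimus: 14 < 28.
- Pasireotide, counted conservatively from the last injection and with the 3-day window used in full: (28 + 3) + 14 = 45 < 56.

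**The case against.** The strongest objection is Figure 6-2, the liver-test algorithm. The branch cites it, and it is missing only because figures were lost in text extraction. It may contain a bilirubin condition on restart, an interruption at ALT/AST 3-5 x ULN, or both. This stands, and it confines the point to the printed text. It does not remove the point: if the figure is stricter, text and figure conflict and need aligning.

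Second, the text prints no interruption at ALT/AST 3-5 x ULN in this branch. The illustrative patient therefore restarts into a state that the text appears to allow on drug under close monitoring. This stands in part. It means that the restart rule and the 3-5 x ULN rule should be settled together. A reader might go further and infer that the plan wrongly omits an interruption at 3-5 x ULN. The documents do not support that while the figure is unseen.

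Third, the 5 x ULN limit fits the 5-8 x ULN criterion and may have been written for it. That is plausible. But the bullet is printed under the bilirubin heading, and a patient can meet both criteria at once.

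Fourth, there are safeguards: restart is permitted rather than required, bilirubin is retested every 3-4 days, and the sponsor is told at once. The two-week rule, the retest sentence, the grade 3 rule in 6.3.2 for drug-attributed changes and the investigator's discretion in 7.1.4.1 also apply. A reader might infer that bilirubin is ignored altogether, or that re-exposure is open-ended. Neither is supported. These provisions limit duration, but none sets a bilirubin condition on the restart itself.

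**Conclusion.** The concern holds for the printed text of 6.1.4.10, at minor severity. In the branch with ALP at or above 2 x ULN, a patient whose drug was interrupted may restart at the original dose on ALT/AST alone, even if bilirubin is still at or above 2 x ULN.

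The 10 to 11 days are an upper bound on the assumptions listed above. One of them matters most: the two-week rule does not name the analytes that must resolve. Entry requires bilirubin no higher than 1.5 x ULN (Section 5.2), so bilirubin still at or above 2 x ULN is not back at an eligible baseline. Counting bilirubin is therefore the natural reading. No frequency is given; the Amendment 5 rationale reports 11 patients still on treatment in the extension.

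The point does not extend to patients with ALP below 2 x ULN. They are discontinued under 6.1.4.10, 6.3.2.1 and 7.1.4.1, and 6.3.2.1 bars re-challenge.

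**What to change.** Reword the restart bullet so that study drug may restart at the original dose only when ALT and AST are both below 5 x ULN and total bilirubin is below 2 x ULN. Bilirubin below 2 x ULN is enough to clear the combined criterion, so the ALT/AST limit need not be lowered to 3 x ULN.

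Then make the text and Figure 6-2 agree, including whether drug is held at ALT/AST 3-5 x ULN in this branch. Leave the two-week rule and the discontinuation criteria unchanged, so that the re-challenge ban is not extended to this pattern.

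The cost is one changed bullet and a check of the figure. No new tests are needed, because bilirubin is already in the repeated panel. The downside is that a few patients stay off drug longer, at most until the two-week rule applies, which is within both delay limits.

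As a separate editorial item, five references to Section 6.1.5 for liver-test rules should point to 6.1.4.10: two in 6.3.1.1, and one each in 6.3.2.1, Table 7-1 and Table 7-2. Section 6.1.5 now only refers on to Section 6.3.
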